12.4 Level of Significance

Inferential statistics will be performed at a nominal level of significance of 0.05 (two-sided). Due to the exploratory character of the analyses, the resulting p-values will not be adjusted for multiple testing.

12.5 Biometric Concept

The general biometric approach consists of the realization of the analyses described in section 7 “Study Objectives”. The analysis principally uses descriptive statistical methods, supported by regression statistical methods and subgroup analysis.

By forward and backward stepwise regression, those patient and disease characteristics (baseline values of all target parameters, disease duration, previous therapies, demographic and anthropometric data, health-related quality of life etc.) will be selected which show a statistically significant partial correlation with the parameters of therapeutic success at month 3 (improvements in the number of affected joints [DAS28], HAQ, number of missed working days, and WPAI). Due to the clear temporal relation between the baseline values and the treatment effects at month 3, the selected predictors can be interpreted both as causal explanation and as prognosing factors concerning therapy-modifying influencing variables (since an reactive influence of the 3-month values on the baseline values can be ruled out). Additionally, the strength of the relationship between the predictors and the parameters of therapeutic success will be determined.

The impact of the features determined by regression analysis on the therapeutic success will be illustrated by subgroup analysis. Subgrouping will be done according to content-related considerations: Regarding disease activity, patients will be classified into groups with high or low DAS28 values (lower and higher 5.1 units, respectively). Regarding age, patients will be classified into groups with high or low age (lower and higher 40 years, respectively).

The impact of adalimumab therapy on health-related quality of life (EQ-5D), the number of physician visits and hospitalizations, the days of impairment in non-occupational activities, and the subjective symptoms (morning stiffness, pain, exhaustion/fatigue) will be descriptively evaluated and additionally analyzed by between-group comparison.

The tolerability analysis will be based on MedDRA coded AEs and SAEs. Incidence rates will be reported on the “Preferred Term” and “System Organ Class” levels for all patients as well as for subgroups of patients with different degrees of disease activity as well as with different previous and concomitant therapies and diseases.

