## 1.10 Biometrics concept of AGIL-CV

*Biometrics concept as an addition to AGIL-CV:*

Using stepwise regression analyses with forward and backward techniques, all partial correlations between the primary parameters and the other disease and patient characteristics are determined at baseline. The impact of disease and patient characteristics on the changes in each of the primary parameters is established by means of these regression analyses at Months 12, 24 and 60. In particular, the DAS28 response (defined as the critical difference [dcrit] of  $\leq -1.8$  points, constituting an improvement of 1.8 points in DAS28) or DAS28 nonresponse was used as a coded variable.

In addition, the observed difference between the DAS28 responders (patients with a dcrit of  $\leq -1.8$  at 5 of 7 visits) and the DAS28 nonresponders (dcrit  $> -1.8$ ) is tested using the general linear model. Missing data are replaced using the Last observation carried forward (LOCF) method.

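### Stepwise selection followed by estimation, apparently on the same data, makes false predictors likely at any sample size and inflates effects and explained variance mainly in the small samples

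*Combined protocol and SAP*

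**What the plan says.** The main plan (Combined protocol and SAP), section 12.5, repeated in its synopsis, sets out three steps.

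- **Selection.** "By forward and backward stepwise regression, those patient and disease characteristics" are picked that meet a significance rule: they "will be selected which show a statistically significant partial correlation with the parameters of therapeutic success at month 3". The candidate list is open. It names "baseline values of all target parameters, disease duration, previous therapies, demographic and anthropometric data, health-related quality of life etc" and stops there.
- **Estimation.** After selection, "the strength of the relationship between the predictors and the parameters of therapeutic success will be determined". No hold-out sample, cross-validation, bootstrap or shrinkage is described.
- **Interpretation.** The plan states that "the selected predictors can be interpreted both as causal explanation and as prognosing factors", because baseline precedes Month 3.

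Section 12.4 sets a nominal two-sided level of 0.05 and says that, as the analyses are exploratory, "the resulting p-values will not be adjusted for multiple testing". Section 12 leaves the detail to a separate SAP, to be approved before the database is opened for the first interim analysis.

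The AGIL-CV amendment (Protocol), section 1.10, follows the same route: "Using stepwise regression analyses with forward and backward techniques", it relates the cardiovascular and metabolic parameters to disease and patient characteristics at baseline, and their changes at Months 12, 24 and 60.

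**The concern.** A p-value or interval from the final stepwise model is calculated as if that model had been fixed in advance. In fact each term is there because it passed a significance test on the same data. Three consequences are possible: null variables enter as predictors, retained true effects are overstated, and explained variance is too high.

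Section 6 of the main plan says the patient numbers allow the impact of disease and patient characteristics to be identified and quantified, so these regressions serve a stated purpose. Section 12.5 also lets the selected terms be read as causal and carries them into subgroup illustrations. A falsely selected variable could therefore be reported as a cause of treatment success. Temporal order rules out reverse influence; it does not protect against chance selection.

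**Working it through.** The documents give no figure for the regressions, so there is none to reproduce. The check asks how large each consequence is at the sample sizes the documents imply.

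**Inputs from the documents**
- Main cohort: about 2500 (main plan, section 12.1).
- Work outcomes: 30% employed, so 0.30 × 2500 = 750 (same section).
- AGIL-CV: 300, with about 50% discontinuing by Month 60 (amendment, section 1.9), so 0.50 × 300 = 150. If the last-observation-carried-forward sentence in section 1.10 covers the regressions, up to 300 stay in.
- Level: 0.05 two-sided (main plan, section 12.4).

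**Assumptions.** 30 independent standardised candidates, three with a true effect of 0.15 SD and 27 null; residual SD 1; entry and removal at 0.05. Other settings are shown below.

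**1. False selection.** Expected number of false predictors ≈ 27 × 0.05 = 1.35. Chance of at least one ≈ 1 − 0.95^27 = 75%. Neither expression contains n. Simulated stepwise runs give about 60–75% from n=150 to n=2500.

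For other list lengths, simulations with candidate correlation 0.2, two effects of 0.3 SD, five of 0.07 SD and the rest null gave:

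| Candidates | n=150 | n=300 | n=750 | n=2500 |
|---|---|---|---|---|
| 15 | 37% | 41% | 41% | 36% |
| 30 | 72% | 67% | 75% | 70% |
| 50 | 88% | 93% | 89% | 89% |

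The rate follows the length of the list, not the sample size.

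**2. Interval coverage.** At n=2500 all three true terms are selected and covered about 95% of the time, while selected null terms are almost never covered. Pooled coverage ≈ (3 × 0.95)/(3 + 1.35) = 66%; simulation gives about 69%. At n=150, where true terms are often missed, simulation gives about 47%. Retained true terms are covered about 95% of the time, so the shortfall comes mainly from null terms. In the mixed setting above, coverage is 77–92% at n=2500 and 75–91% at n=750. A full model fitted to the same kind of data covers about 95% at every n.

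**3. Inflation of retained true effects.** With λ = β√n and c = 1.96, the expected overstatement given selection is approximately 1 + φ(c−λ)/{λ[1−Φ(c−λ)]}.

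| β (SD) | n | λ | Formula | Simulation |
|---|---|---|---|---|
| 0.15 | 150 | 1.84 | 1.48 | 1.46 |
| 0.15 | 300 | 2.60 | 1.17 | 1.18 |
| 0.15 | 750 | 4.11 | 1.01 | about 1.0 |
| 0.15 | 2500 | 7.50 | 1.00 | about 1.0 |
| 0.07 | 750 | 1.92 | 1.43 | 1.45 (1.57 at correlation 0.2) |
| 0.07 | 2500 | 3.50 | 1.04 | 1.03 (1.07 at correlation 0.2) |

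**4. Explained variance.** True R² = 3 × 0.15² / (1 + 3 × 0.15²) = 0.0675/1.0675 = 6.3%. Apparent R² after selection is about 11% at n=150, 9% at n=300 and 6.7% at n=2500. In the mixed setting with 30 candidates, apparent R² against the R² the same fitted model would reach in new patients is 0.301 against 0.174 (n=150), 0.280 against 0.214 (n=300), 0.265 against 0.236 (n=750) and 0.259 against 0.251 (n=2500).

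**The case against.** The strongest reply has four parts.

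- **The cohort is large and the analyses are exploratory.** Size does remove most of the inflation, as steps 3 and 4 show. It does not remove false selection. The exploratory label in section 12.4 waives multiplicity adjustment; it does not correct intervals computed as if the model had been fixed, and it sits badly with the causal reading in section 12.5.
- **The detail is deferred.** The announced SAP could add validation, and it is not among the documents. But the stepwise method is already stated, and an SAP that only detailed it would inherit the problem.
- **The plan does not promise these outputs.** This stands in part. Section 12.5 names neither confidence intervals nor R², only strength of relationship, and use of the same data is inferred because no other data set is mentioned. The amendment refers to all partial correlations at baseline, so reporting there may not be limited to selected terms. The subgroup cut-points given (DAS28 of 5.1, age 40) are fixed in advance, which limits how far selection carries into those illustrations.
- **AGIL-CV may not fall to 150.** This also stands. The scope of the carry-forward sentence is unclear, so 150 and 300 are both shown.

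A reader might infer that every reported effect and R² in the main cohort will be too favourable, or that the intervals of genuine predictors fail badly. The documents do not support that. Near n=2500, effects of 0.15 SD are essentially unbiased and R² is about right, and the low pooled coverage comes mainly from null terms.

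**Conclusion.** The concern holds in a limited form. Following the plan as written gives p-values and intervals that ignore selection, and at least one false predictor is more likely than not with about 30 candidates, whatever the sample size. Overstated effects and explained variance are material in AGIL-CV at Month 60, and for weak effects (0.07 SD) in the work outcomes at about 750 patients. They are negligible near 2500 for effects of 0.15 SD.

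All sizes rest on assumed numbers of candidates, correlations and effect sizes, because the list is open and the documents give no effect sizes. With 15 candidates the false-selection rate falls to about 36–41%; with 50 it rises to about 88–93%. The direction does not depend on these choices. The change should be made, and it is a cheap improvement.

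**What to change.** 1. Close the candidate list for each outcome in the SAP before the first interim analysis. A full model cannot be specified from an open list, so this comes first.
2. Fit one prespecified model per outcome with all listed candidates, and report every coefficient with its 95% CI. With 30 candidates this leaves about 83 patients per candidate at n=2500 and 25 at n=750.
3. In AGIL-CV, where 30 candidates would leave 5 to 10 patients each at Month 60, use a penalised model and report bootstrap optimism-corrected R². State whether carry-forward applies to these regressions.
4. If stepwise selection is kept, label it screening only, report bootstrap selection frequencies instead of p-values, and delete the statement that selected predictors can be read as causal explanation.

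The cost is SAP wording and routine software; no new data are needed. The downside is wider intervals and fewer predictors reaching significance. Penalisation with the bootstrap is one workable choice among several.

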Course of work productivity and work ability, the course of health-related quality of life, and changes in functionality under long term treatment with adalimumab will be documented. The numbers of patients included in the NIS allow identifying and quantifying the impact of disease and patient characteristics on the therapeutic success.

7 Study Objectives

In this NIS, a long term documentation of treatment with adalimumab in RA patients over 60 months with 8 data collection points (visits) is planned. The documentation will be performed by the physician as well as by patient's self-assessment.

The primary objective is to explore the therapeutic success by interim analyses after 12 and 24 months of treatment as well as by the final analysis after 60 months of treatment. Improvements concerning the following target variables will be evaluated (with regard to the respective baseline value):

- the number of missed working days
- the self-assessed work ability (WPAI)
- the severity of clinical symptoms (number of tender and swollen joints, CRP and ESR, respectively; total score DAS28)
- Severity of functional impairment (HAQ)
- The health-related quality of life (EQ-5D)

At month 3, patient and disease characteristics will be evaluated with regard to their additional impact on changes in the number of affected joints (DAS28), in the HAQ, and in the WPAI. The impact on the number of missed working days will be evaluated at month 6.

The secondary objective is to document the therapeutic success by interim analyses at month 12 and 24 months as well as by the final analysis after 60 months. The therapeutic success will be evaluated by the following variables:

- The number of physician visits
- The number and duration of hospitalizations
- The number of days of impairment in non-occupational activities
- The duration of morning stiffness, pain, exhaustion/fatigue

- The reduction of number and dose of concomitant medication
- Patient's assessment of adalimumab therapy compared to previous therapies

Target parameters for safety evaluation of adalimumab are:

- The evaluation of safety and tolerability by the documentation and analysis of serious adverse events (SAEs) and adverse events (AEs).
- Evaluation of safety and tolerability for subgroups of patients with common frequent concomitant diseases, especially diabetes type II, cardiovascular, liver, and renal insufficiencies, and related concomitant medications.

8 Investigational Plan

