12.1 Sample Size Calculation

The primary parameter of this documentation is work productivity, which is captured by the number of missed working days. The sample size calculation is based on the results of an interim analysis of a documentation of adalimumab in RA with 4640 patients, of whom 1417 patients had been employed part time or full time. The mean number of missed working days was 26 days (standard deviation of 55 days) during the last 12 month prior to adalimumab therapy. The correlation between baseline and follow-up report is estimated with $r = 0.5$. According to these numbers, 850 employed patients are required to detect a mean difference of 5 days within 12 months at the 0.05 significance level (two-sided) with a power of 0.80. Since 30 % of patients are employed, a total number of about 2500 employed and non-employed patients are required in order to detect the specified difference in missed working days.

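### Predictors of improvement in missed working days are selected by a linear-model significance test with no variance-robust standard error, so the nominal 5% can be too high or too low where sick-leave level differs between unequal groups

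*Combined protocol and SAP*

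**What the plan says.** All references are to the AGIL documentation plan (the combined protocol and SAP).

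- **Section 12.5** passes improvement in joint counts (DAS28), HAQ, WPAI and missed working days through the same stepwise regression, forward and backward. It keeps baseline characteristics that show a "statistically significant partial correlation with the parameters of therapeutic success" at month 3. Baseline values of all target parameters are among the candidates, so baseline missed days are too. Selected predictors may be read as causal and as prognostic, their strength is reported, and they feed the subgroup analysis. No transformation, count model, robust standard error or bootstrap is mentioned.
- **Section 12.1** calls missed working days the primary parameter and states: "The mean number of missed working days was 26 days (standard deviation of 55 days) during the last 12 month prior to adalimumab therapy".
- **Section 12.4** sets a nominal two-sided 0.05 level, calls the analyses exploratory and makes no multiplicity adjustment.
- **Section 12** leaves the details to a separate SAP, to be finalised before the first interim analysis.
- **Section 7** gives a different time point from 12.5: "The impact on the number of missed working days will be evaluated at month 6".

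**The concern.** A partial-correlation test with ordinary standard errors assumes the same residual variance for every patient. Missed working days cannot be negative, and an SD of twice the mean points to many low values and a few very long absences. For such a variable, groups with more sick leave normally also vary more. If a candidate predictor (say, previous biologic therapy or long disease duration) marks a small group with more sick leave, the pooled variance understates that group's uncertainty and the predictor is selected too often. If it marks a small group with less sick leave, a real association tends to be missed.

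This is distinct from the known weakness of stepwise selection, because it affects even a single predictor named in advance. At stake are the list of predictors that the plan intends to interpret causally, their reported strength, and the subgroup displays built on them.

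**Working it through.** **1. The plan's own sample size.** This only fixes a realistic n for the check. Inputs from 12.1: SD 55, correlation of the two reports r = 0.5, two-sided alpha 0.05 and 80% power. The stated result is "850 employed patients are required to detect a mean difference of 5 days within 12 months".

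- Variance of change = 2 × 55² × (1 − 0.5) = 3025.
- n = (1.960 + 0.842)² × 3025 / 5² ≈ 950, so the stated 850 does not reproduce.
- 30% of 2500 is 750 employed patients.

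That discrepancy is a separate matter. The checks below use 750 or 850, and the result in step 4 does not depend on n.

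**2. Shape.** 55/26 = 2.12. A normal distribution with this mean and SD would put Φ(−26/55) = Φ(−0.47), about 32%, below zero, which is impossible for days. The variable must be strongly right-skewed. Under the distributions assumed below, the top 10% of patients hold about 58-70% of all missed days.

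**3. Does skew alone break the test?** Assumed: zero-inflated gamma days (50% zeros, mean 26, SD 55, r about 0.5, skewness about 3.7), with a predictor unrelated to missed days. The ordinary test of change, with and without baseline in the model, rejected in 4.5-5.7% of runs at n = 850 and 4.6-5.9% at n = 400, even for a predictor held by 3% of patients. Simulation noise is about 1 point. Skew alone does not break it.

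**4. What breaks it: unequal variance with unequal groups.** Let a binary predictor be held by a share p of patients, and let the SD of change in that group be k times the SD in the rest. For the difference in means:

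- assumed variance / true variance = [p·k² + (1 − p)] / [(1 − p)·k² + p]
- real type I error = 2 × [1 − Φ(1.96 × √ratio)]

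Example, p = 0.2 and k = 2: (0.8 + 0.8)/(3.2 + 0.2) = 0.471; √0.471 = 0.69; error 17.9%. A simulation of this case gave 18.0%.

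| Share p | k = 0.5 | k = 1.5 | k = 2 |
|---|---|---|---|
| 10% | 0.09% | 15.4% | 24.5% |
| 20% | 0.4% | 12.1% | 17.9% |
| 50% | 5.0% | 5.0% | 5.0% |

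The sample size cancels, so more patients do not help. These figures assume SD proportional to level, equal mean change and no baseline adjustment. They show the mechanism and its direction. They are not the best estimate of size, because 12.5 makes baseline days available to the model.

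**5. With baseline days in the model, n = 750.** Three sets of assumed distributions were simulated. The level ratio is sick leave in the group relative to the rest.

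| Assumed days | Group | Ordinary test | HC3 |
|---|---|---|---|
| A: gamma capped at 250 (mean about 24, SD 48, r 0.42) | 10%, ratio 0.5 / 1.5 / 2 | 1.4 / 6.6 / 9.9% | 7.9 / 6.0 / 7.1% |
| A | 20%, ratio 0.5 / 1.5 / 2 | 1.8 / 7.3 / 7.8% | 6.1 / 5.3 / 5.8% |
| B: gamma and zero-inflated lognormal | 10-20%, ratio 1.5-2 | 8.5-15.8% | 4.4-7.4% (all B settings) |
| B | 10-20%, ratio 0.5 | 0.6-0.9% | as above |
| B | unrelated predictor, or 50:50 split | about 5% | as above |
| C: gamma | 20%, ratio 1.5-2 | 5.8-6.6% | not run |
| C | 30-50% | 3.2-5.2% | not run |

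**6. Baseline days as a predictor.** Here variance almost certainly changes with the predictor. In set B, ordinary 95% intervals for this coefficient missed the true value in 30-37% of runs. In another assumed model the average ordinary standard error was 0.030 against a true 0.080, with 52% coverage.

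**7. Time point.** Section 12.5 places the missed-days analysis at month 3 and Section 7 at month 6. Table 2 (Patient Schedule) collects missed days, with a 6-month recall, at month 0 and from month 6 on, but not at month 3. The month 3 analysis of this variable therefore has no data.

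**The case against.** **The size is assumed.** The 26 and 55 describe 12-month baseline days. The regression outcome is improvement, the form asks about 6 months, and the documents give no distribution for either. The group ratios of 0.5 to 2 are assumptions. This stands, and it is why the result is conditional and given as a range.

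**The plan may yet specify the method.** The word ordinary does not appear in 12.5, and an SAP was to follow. However, partial correlation is a linear-model criterion and 12.5 already fixes it as the selection rule, so an SAP could simply inherit it.

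**The level is only nominal and exploratory.** Section 12.4 waives adjustment for multiple tests. That does not make a single standard error or interval valid.

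**Stepwise selection does more damage.** With 10 or 20 independent null candidates, the chance of at least one false selection is 1 − 0.95^10 = 40% or 1 − 0.95^20 = 64%, with normal data too. This stands: robust errors do not cure it.

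**The remedy is imperfect.** In set A, HC3 turned a conservative 1.4% into 7.9%. For a predictor held by only 3% of patients and unrelated to missed days, with baseline in the model, HC3 gave 9.0% at n = 850 and 14.4% at n = 400, where the ordinary test gave 5.1% and 5.6%. This also stands and limits the fix.

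**Two stronger readings are tempting.** A reader might infer that the 5% level fails simply because the SD exceeds the mean; step 3 shows that it does not. A reader might also infer that the study's sizing is undermined; 12.1 sizes a within-patient mean change, which this regression does not test.

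**Conclusion.** The point holds in conditional form. For a very probably skewed outcome, 12.5 relies on a linear-model significance criterion and names no protection against unequal variance. The 5% level is kept, or nearly so, for predictors unrelated to sick leave and for roughly even splits. It fails where sick-leave level, and so variance, differs between groups of unequal size.

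With baseline days in the model and n = 750, type I error was roughly 7-16% for groups of 10-20% with 1.5-2 times the sick leave (one milder set gave about 6% for a 20% group) and roughly 0.6-2% for groups with half. The baseline-days coefficient is the clearest case, with intervals far too narrow in every model tried. All of this rests on assumed distributions and group ratios. The unadjusted figures of 12-25% should not be quoted as the expected size. The change is cheap and worth making before the SAP is finalised.

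**What to change.** Add to 12.5, and carry into the SAP: *For missed working days, tests (including those for entry and removal) and 95% intervals use heteroscedasticity-robust (HC3) standard errors or a patient-level bootstrap, with baseline days kept in the model.*

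A log-link negative binomial model of follow-up days with robust standard errors can be reported as an optional sensitivity analysis. It should stay optional: for a predictor held by 30% of patients with a rate ratio of 0.7, it raised power from 39% to 66% under gamma data but gave no gain under zero-inflated data.

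In the same edit, reconcile the month 3 of 12.5 with the month 6 of Section 7 and with Table 2.

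Cost: a sentence, a software option (with some programming if the stepwise routine does not accept robust tests) and no new data. Intervals widen for small groups with high variance. HC3 can be mildly anti-conservative, up to about 7-8%, for groups of 10% and worse for groups of a few percent, so the SAP should state the smallest group for which a test is reported. The problem of false selections by the stepwise procedure remains and needs its own remedy.
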